2.1 Schedule of Assessments

Study Phase	Treatment Period			End-of-Study or Premature Withdrawal ¹⁰
	Baseline ⁶	3-Month Visits ⁸	6-Month Visits	
Study Days (± visit window)	Day 1 (Week 28 of Study HZNP-ACT-302)	90 (± 7) Days after Last Visit	Every 180 (± 14) Days	
Informed consent/assent	X			
Medical history ¹	X			
Review of inclusion/exclusion criteria	X			
Dispense study drug ²	X	X ⁹	X	
Drug compliance ³		X ⁹	X	X
TEAE, SAE assessment ⁴	X ⁷	X	X	X
Brief physical examination	X ⁷		X	X
Vital Signs: blood pressure, pulse, temperature	X		X	X
Clinical laboratory evaluation (hematology, chemistry, urinalysis)	X		X	X
Electrocardiograms				X ¹¹
Urine pregnancy test ⁵	X		X	X
FARS				X ¹¹
Prior/concomitant medications	X ⁷	X	X	X

SAE=serious adverse event, TEAE=treatment-emergent adverse event.

¹ Changes in medical history from the Baseline of HZNP-ACT-301 will be recorded on the electronic case report forms. The medical history from the HZNP-ACT-301 study will be available for reference.

² Subjects will be given a 3-month supply of study drug at each clinic visit and an additional 3-month supply will be directly shipped to the subjects' home in between the required 6-month clinic visits. If direct shipments are not feasible, subjects will return to the clinic every three months to obtain study drug; however, assessments (other than adverse event queries) will only be performed every six months.

³ Subjects will be instructed to return all used and unused study drug vials at each clinic visit.

⁴ Adverse events occurring or worsening on or after the date of administration of the first dose of study drug through the end of the study will be considered treatment-emergent adverse events (TEAEs). All serious adverse events (SAEs) that occur on or after the date of administration of the first dose of study drug through two weeks after study discontinuation will be considered treatment-emergent SAEs (TESAEs) and will be recorded and reported to Horizon drug safety.

⁵ Only for female subjects of childbearing potential.

⁶ The Day 1 Visit of this study (HZNP-ACT-303) occurs on the same day as the EOS Visit (Week 28 Follow-Up Visit) for HZNP-ACT-302.

⁷ Findings will be recorded for both the Day 1 (Baseline) Visit of this study and the Week 28 Follow-up Visit for HZNP-ACT-302.

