8.4.7.3 Details Concerning Timing and Dose Administration

All doses of study drug will be administered by SC injection. Subjects and/or their caregivers will be instructed on their individualized dosing volume and proper dosing techniques; they will also be instructed to administer the study drug on the right and left deltoid, anterior thigh, and upper and lower abdomen and to rotate the injection sites.

Subjects or their caregivers will also be instructed in safe handling and storage of used syringes and needles. The clinical staff will demonstrate proper technique for withdrawing the appropriate volume of study drug from the vial. If two vials are needed to achieve the dose, an equal volume should be removed from each vial. For example, if the dose should be 0.8 mL, then 0.4 mL should be withdrawn from each vial into separate syringes and two injections given. The injection site will be cleaned with an alcohol swab and allowed to air dry. About an inch of skin and fat tissue will be pinched between the thumb and forefinger, the needle will be inserted all the way into the pinched skin, and the entire volume of study drug will be injected under the skin.

Subjects and their caregivers will be instructed to administer study drug on an outpatient basis TIW (e.g., a dosing schedule of Monday, Wednesday and Friday or Tuesday, Thursday, and Saturday) for the duration of the study.

At each clinic visit, subjects and/or their caregivers will be dispensed a 3-month supply of study drug, and an additional 3-month supply will be directly shipped to the subjects' home in between the required 6-month clinic visits. If direct shipments are not feasible, subjects will return to the clinic every three months to obtain study drug. At all post-Baseline clinic visits, subjects and/or their caregivers will return all unused kits and study drug vials.

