8.4.11 Treatment Compliance

Study medication will be dispensed at clinic visits and re-supplies of study drug may be shipped in temperature-controlled containers to the subject's home. All unused study drug received by the subjects since the previous visit will be returned at the subsequent visit for drug accountability.

An inventory of the study medication supplies will be performed by the site or authorized study designee and recorded onto the Drug Accountability Log in the subject's source document records or equivalent.

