8.5.4.1 Baseline/Day 1 (Week 28 of Study HZNP-ACT-302)

The Baseline/Day 1 Visit of this study (HZNP-ACT-303) occurs on the same day as the EOS Visit (Week 28 Follow-Up Visit) for HZNP-ACT-302. At the Baseline Visit, study drug will be

distributed for administration at home according to the planned TIW dosing schedule. Clinic staff will perform the following procedures:

- Obtain signed, written Informed Consent/Assent and permission to use Protected Health Information (in accordance with the Health Insurance Portability and Accountability Act [HIPAA]) for Study HZNP-ACT-303. Refusal to provide this permission excludes an individual from eligibility for study participation. Record date Informed Consent/Assent was given and who conducted the process on the appropriate source documentation.
- Perform review of inclusion/exclusion criteria.
- Record any changes in medical history since Baseline of HZNP-ACT-301.
- Perform brief physical examination¹, including vital signs.
- Enquire about adverse events¹ and concomitant medications¹.
- Collect blood (4.5 mL) and urine samples for safety clinical laboratory values (including urine pregnancy test [if applicable]).
- Dispense a 3-month supply of study drug.

¹ Findings will be recorded for Day 1 (Baseline) of this study and for the EOS Visit (Week 28) of previous study (HZNP-ACT-302).

Subjects will be discharged from the study center after all of the Study Day 1 procedures have been completed. Subjects who are able to receive study drug shipped directly to their home will be instructed to return to the clinic in six months, and those who are not able to receive study drug shipments at home will be instructed to return in three months.

8.5.4.2 3-Month Visits

Subjects who are able to receive direct-to-home shipments of study drug will be contacted by phone three months after the Baseline and 6-month assessment visits and queried regarding adverse events and concomitant medication use.

Subjects who are not able to receive study drug shipments at their home will return to the clinic for interim clinic visits three months after the Baseline and 6-month assessment visits, and clinic staff will perform the following assessments:

- Collect all used, partially used, and unused study medication kits and vials from the previous clinic visit.
- Enquire about adverse events and concomitant medication use
- Dispense a 3-month supply of study drug.

8.5.4.3 6-Month Assessment Clinic Visits

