- Collect all used, partially used, and unused study medication kits and vials from previous clinic visit.
- Perform brief physical examination, including vital signs.
- Collect blood (4.5 mL) and urine samples for safety clinical laboratory values (including urine pregnancy test [if applicable]).
- Enquire about adverse events and concomitant medication use.
- Dispense a 3-month supply of study drug.

Subjects will be released from the study center after all of the visit procedures have been completed and instructed to return to the clinic in three or six months, as applicable.

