6.3 Derived and Computed Variables

The following derived and computed variables have been initially identified as important for the analyses of Safety and Efficacy endpoints. It is expected that additional variables may be required. The SAP will not be amended for additional variables that are not related to the primary target or key secondary target variables. Any additional derived or computed variables will be identified and documented in the SAS programs that create the analysis files. If the SAP is not amended, further derivations related to primary and secondary target variables will be described in the CSR.

- 303 Baseline = The last non-missing measurement/assessment on the date of Week 26
 Visit from HZNP-ACT-302. If this measurement is missing or otherwise unavailable, it
 will be the last non-missing measurement/assessment on or prior to first dose in HZNP ACT-303.
- Study Day = Assessment Date Date of Enrollment + 1
- Change from Baseline = Value at Post-Baseline Value at Baseline
- Concomitant Medication is defined as any medication a subject has received concurrently with study treatment.
- Prior Medication is defined as any medication or therapies initiated prior to date of first dose of study drug. Medications that are started prior to the date of first dose of study drug and continue after the first dose of drug are considered to be both prior and concomitant medications.
- Treatment-Emergent Adverse Event (TEAE) A TEAE is any adverse change from the subject's baseline condition that occurs on or after the date of the first dose of study drug through the duration of the clinical study.
- Related TEAE Any TEAE with a reported relationship to study drug of 'possibly related'.
- Compliance = Calculated as the percentage of the number of vials used divided by the expected number of vials used, where the number of vials used is the number of used vials returned.

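### The SAP scores every unreturned used vial as a missed dose, and the protocol's return instructions conflict

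*SAP*

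**What the plan says.** SAP 6.3 defines compliance as "Calculated as the percentage of the number of vials used divided by the expected number of vials used", and then fixes the numerator: "where the number of vials used is the number of used vials returned". It does not define the expected number and gives no rule for vials that never come back. SAP 9.6 summarises compliance and exposure over the whole study and lists both with drug accountability by subject.

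The protocol gives sites and families several return instructions.

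- Schedule of Assessments, footnote 3 (repeated in SAP Table 1): "Subjects will be instructed to return all used and unused study drug vials at each clinic visit".
- Section 8.5.4.2, 3-month clinic visit: "Collect all used, partially used, and unused study medication kits and vials from the previous clinic visit".
- Sections 8.5.4.3 and 8.5.4.4, 6-month and end-of-study visits: "Collect all used, partially used, and unused study medication kits and vials from previous clinic visit".
- Section 8.4.6: the site keeps empty and part-empty vials, as well as full ones, until accountability is finished.
- Footnote 9: subjects with telephone visits bring supplies back at their next clinic visit.
- Section 8.4.11, Treatment Compliance: "All unused study drug received by the subjects since the previous visit will be returned at the subsequent visit for drug accountability". Used vials are not mentioned.
- Section 8.4.7.3: "At all post-Baseline clinic visits, subjects and/or their caregivers will return all unused kits and study drug vials". This can mean unused kits and unused vials, or unused kits and all vials.

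**The concern.** The numerator measures two things at once: whether the dose was taken, and whether the empty vial was brought back. A family that discards empties looks the same as a family that skips injections. The error runs one way, downward. The protocol section that bears the name of the variable does not ask for the items that the SAP counts.

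The study's only objective is long-term safety, dosing is at home and treatment is open-ended. The documents describe no dosing diary, and SAP 6.3 defines compliance but gives no derivation for exposure. The vial ratio is therefore the only defined measure of how much drug was actually taken. If it reads low, the adverse event rates may be taken to represent less treatment than subjects received.

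**Working it through.** The documents state no compliance figure or threshold, so there is nothing to reproduce. The check is direct arithmetic on the SAP 6.3 formula.

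**Inputs**

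- Three doses a week (Protocol 8.4.7.3).
- One or two vials per dose (Protocol 8.4.2.1). Two is realistic: the worked example in 8.4.7.2 gives 0.705 mL, and a vial yields up to 0.5 mL.
- One three-month supply from the clinic and one shipped home in each six-month interval (Schedule of Assessments, footnote 2).
- Assumption, because the SAP is silent: expected vials = 3 x weeks x vials per dose, with 13 + 13 weeks per interval.

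**Step 1: structure of the score.** Let E be vials expected, U vials actually used and R used vials returned. Then

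score = 100 x R/E = 100 x (U/E) x (R/U),

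which is true compliance times the return fraction. At full dosing, a return fraction of 90% scores 90%, and 75% scores 75%. At 80% true compliance with 75% of empties returned, the score is 0.80 x 0.75 = 60%.

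**Step 2: a fully dosed subject over 26 weeks.** Doses: 3 x 26 = 78. Vials: 78 at one per dose, 156 at two. One three-month supply: 3 x 13 = 39 doses, so 39 or 78 vials.

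| Empties returned | One vial per dose | Two vials per dose | Score |
|---|---|---|---|
| All | 78/78 | 156/156 | 100% |
| One of the two supplies | 39/78 | 78/156 | 50% |
| None, counted as zero | 0/78 | 0/156 | 0% |

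Using 90 and 180 days instead of 13 and 26 weeks still gives 50% in the middle row. Over a longer stay the effect is diluted: 52 weeks is 3 x 52 = 156 doses, and one unreturned supply gives (156 - 39)/156 = 75%.

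**Step 3: the obvious alternative has the opposite bias.** Take 78 vials dispensed and expected, at one per dose. Unaccounted vials are 78 minus used returned minus unused returned.

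| Truly used | Used returned | Unused returned | SAP score | Dispensed minus unused | Unaccounted | Truth |
|---|---|---|---|---|---|---|
| 78 | 39 | 0 | 50% | 100% | 39 | 100% |
| 62 | 62 | 16 | 79.5% | 79.5% | 0 | 79.5% |
| 62 | 0 | 16 | 0% | 79.5% | 62 | 79.5% |
| 62 | 0 | 0 | 0% | 100% | 78 | 79.5% |

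The truth lies between the two figures in every row, and they agree when nothing is unaccounted for. Neither is safe alone, but together they bracket the answer.

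**Step 4: the denominator.** Vials per dose cancels only while it stays constant, and the investigator may change the dose. A fully dosed subject with 13 weeks at one vial and 13 at two uses 39 + 78 = 117 vials. With all empties returned, the score is 117/78 = 150% if one vial per dose is assumed throughout, and 117/156 = 75% if two. Expected vials must therefore be built up by period.

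**The case against.** The SAP numerator matches most of the protocol. Footnote 3, the SAP's own schedule and every post-Baseline clinic-visit procedure call for used vials, and the site keeps the empties. A reader of 8.4.11 might infer that the trial collects only unused drug, so that the numerator would be zero by design. The documents do not support that. Section 8.4.11 is the one clear outlier, 8.4.7.3 can be read either way, and a zero numerator needs sites to disregard section 8.5.4.

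Four other strong readings also fail.

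- A reader might take the 50% as a consequence of the conflicting sections. It is not: it needs the separate premise that one supply of empties stays at home. The visit procedures' reference to vials from the previous clinic visit could encourage that for home-shipped drug, but footnote 9 points the other way.
- A reader might infer that a subject lost to follow-up is scored 0%. SAP 6.2 says other missing data are not imputed unless specified, so an absent count could equally be left missing.
- A reader might conclude that exposure cannot be read at all. That goes too far, since SAP 9.6 also provides exposure and an accountability listing by subject, and dose changes are recorded on the eCRF.
- A reader might assume that every count for a better formula is already in the site's accountability records. Section 8.4.6 speaks of medication shipped to the study center, while home shipments come from the supply vendor (8.4.3, 8.4.7.1).

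What survives is the formula. Clear instructions reduce unreturned empties, but the SAP still scores each one as a dose not taken.

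**Conclusion.** The point holds as a one-sided measure combined with an internal conflict. SAP 6.3 biases compliance downward by exactly the fraction of used vials not returned, and the protocol does not ask consistently for those vials. The 50% and 0% figures illustrate what the formula can produce. They are not forecasts, because the documents give no return rate. The 0% also assumes that an absent return is counted as zero. All the percentages rest on the assumed definition of expected vials.

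No hypothesis test is planned, the only analysis population is the Safety Population, and no compliance threshold is set. No planned result changes, and the damage is confined to how the adherence summary is read. Severity is minor to moderate.

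**What to change.** In SAP 6.3, replace the single ratio with three figures:

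- (a) used vials returned / expected vials, labelled a lower bound;
- (b) (vials dispensed + vials shipped - unused vials returned) / expected vials, labelled an upper bound;
- (c) the number of unaccounted vials, which is the difference between the numerators of (b) and (a).

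Treat a subject with no return record as unaccounted, not as 0% compliant. Compute expected vials by period from the recorded dose and the vials needed per dose. State how partially used vials count, since the visit procedures separate them from used vials and the SAP does not.

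In the protocol, reconcile 8.4.11 and 8.4.7.3 with footnote 3 and section 8.5.4, and make clear that home-shipped vials are included in the returns. The SAP change is worth making even if the protocol can no longer be amended.

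The cost is one or two extra lines in the compliance table and wording in two protocol sections. Direct-to-home quantities may have to come from the supply vendor's shipment records, which would add a data transfer.

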7. STUDY SUBJECTS AND DEMOGRAPHICS

7.1 Disposition of Subjects and Withdrawals

All subjects who provide informed consent/assent will be accounted for in this study. The number of subjects enrolled, completing, and withdrawing from the study, as well as reason for withdrawal, will be summarized by overall treatment. All disposition information will be included in a listing.

7.2 Protocol Violations and Deviations

Protocol deviations will be collected by the clinical team and provided to Premier biostatistics prior to database lock. Deviations will be reviewed on a case-by-case basis to be classified as major or minor by the project team prior to database lock. Major and minor deviations will be

Protocol: HZNP-ACT-303 Page 13 of 19

Final Version 1.0

included in a listing.

7.3 Demographics and Other Baseline Characteristics

Descriptive summaries and frequencies/percentages of demographic and other baseline characteristics will be completed for all enrolled subjects in the safety population for data collected in HZNP-ACT-301. These tabulations will include the following variables:

• Demographics (age, age categories (10-16 inclusive, and 17 and above), gender, race, ethnicity, height, weight, and Body Surface Area (BSA))

Tabulations of baseline HZNP-ACT-301 efficacy assessments will include the following in a separate table:

- FA Functional Stage
- FARS-mNeuro score
- ADL
- T25FW
- FARStot

Descriptive summaries and frequencies/percentages of demographic and other baseline conditions in separate tabulations will include the following:

- Medical History
- Prior Medications
- Baseline Physical Examination

Medical History: Incidences of findings in medical history will be summarized by System Organ Class and preferred term.

Prior Medications: The frequency and percentage of all prior medications will be summarized by Anatomical Therapeutic Chemical (ATC) classifications level 3 and preferred term for all subjects. Subjects will only be counted once within ATC and preferred term. These data will be grouped by overall treatment.

Baseline physical examination: Baseline physical examination will be summarized by body system and result by overall treatment.

8. EFFICACY ANALYSIS

All analyses are being conducted for an abbreviated safety CSR, and no efficacy analysis will be carried out.

9. SAFETY AND TOLERABILITY ANALYSIS

The analysis of safety assessments in this study will include summaries of the following categories of safety and tolerability data collected for each subject:

- Adverse Events
 - Summary of all Adverse Events
 - o TEAEs, and Serious Adverse Events (SAEs)
 - o TEAEs by severity
 - o TEAEs by relationship to study drug
 - o TEAEs leading to premature withdrawal

Protocol: HZNP-ACT-303 Page 14 of 19

Final Version 1.0

- o Any deaths
- Clinical Laboratory Investigations
 - o Complete Blood Count
 - Chemistry panel
 - Urinalysis
- Electrocardiograms (ECG)
- Echocardiograms
- Physical Examinations
- Concomitant Medications
- Study Drug Exposure and Treatment Compliance

All tabulations and summaries for these categories will be performed on the safety population unless otherwise noted.

9.1 Adverse Events

Missing and partially missing AE start and/or stop dates will be imputed for the purpose of statistical analysis, according to the specifications described in Section 6.2.

A summary of overall TEAEs, TEAEs, SAEs, TEAEs leading to PW, TEAEs by relationship to study drug, and severity of TEAEs will be presented by overall treatment.

Summaries and incidence rates (frequencies and percentages) of individual TEAEs by MedDRA System Organ Class (SOC) and preferred term will be displayed by overall treatment received. Such summaries will be displayed for TEAEs, SAEs, TEAEs leading to early termination, TEAEs by relationship to study drug, and TEAEs by severity

Each subject will be counted only once within each preferred term. If a subject experiences more than one TEAE within a preferred term only the TEAE with the strongest relationship or the maximum intensity, as appropriate, will be included in the summaries of relationship and intensity. No inferential statistical tests will be performed.

In the AE data listings, all AEs will be displayed.

9.1.1 Deaths

A summary and data listing of deaths that occurred will be provided, displaying details of the event(s) captured on the CRF.

9.2 Clinical Laboratory Evaluations

Descriptive summaries of actual (absolute) values and changes from baseline will be presented for Chemistry, Urinalysis, and Complete Blood Count. These tables will be grouped by visit, and overall treatment.

The number and proportion of subjects with clinical laboratory values below, within, or above normal ranges, at each study visit will be tabulated (shift tables) for each clinical laboratory analyte by treatment group. Normal ranges will be provided by the central laboratory (Eurofins Central Laboratory) used in this study.

Laboratory values will be displayed in data listings and those that are outside the normal range will be flagged, along with the corresponding normal ranges.

Protocol: HZNP-ACT-303 Page 15 of 19

Final Version 1.0

9.3 Vital Signs

Descriptive summaries of actual (absolute) values and changes from baseline will be presented for all vital signs (temperature, systolic blood pressure, diastolic blood pressure, heart rate), weight, height, and BSA will be presented by visit and overall treatment. These data will be presented in a data listing by subject.

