Overall, the safety profile of ACTIMMUNE in FA subjects in this IIS mirrors the typical profile and frequency of adverse events in the prescribing information for ACTIMMUNE. In two cases, the maintenance dose of ACTIMMUNE was lower than planned in response to either raised liver function tests and/or flu-like symptoms. Subjects were able to continue in the study following dose reduction.

Based on the results of the IIS, Horizon is currently conducting two studies with ACTIMMUNE. The first study (HZNP-ACT-301) is a randomized, multicenter, double-blind, placebo-controlled

26-week study evaluating the efficacy and safety of ACTIMMUNE administered to children and young adults with FA, and the second study (HZNP-ACT-302) is an open-label 26-week efficacy and safety extension of HZNP-ACT-301, in which all subjects who complete blinded treatment in HZNP-ACT-301 will be offered the opportunity to receive ACTIMMUNE for an additional 26 weeks. As of 10 March 2016, 14 subjects had completed HZNP-ACT-301 and enrolled in HZNP-ACT-302, and it is projected that the first subject will complete HZNP-ACT-302 in June of 2016. Therefore, the Sponsor has designed this protocol to collect long-term safety data and to offer subjects who complete HZNP-ACT-302 the opportunity to continue receiving ACTIMMUNE until it is commercially available for the treatment of FA in the US or until the Sponsor decides to discontinue development for this indication.

FA is a rare, debilitating, autosomal recessive deoxyribonucleic acid (DNA)-inherited, mitochondrial disease that causes progressive damage to the nervous system. The rationale for use of ACTIMMUNE for the treatment of FA is based on *in vitro* and animal data, and clinical experience in FA subjects. Currently, there is no FDA-approved therapy for FA. ACTIMMUNE was granted Orphan Drug Designation for the treatment of FA on October 1, 2014.

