8.3 Selection of Study Population

8.3.1 Inclusion Criteria

Eligible subjects must meet all of the following criteria:

1. Written informed consent and child assent, if applicable.
2. Completed 26 weeks of treatment and the Week 28 Follow-Up Visit in Study HZNP-ACT-302.
3. If female, the subject is not pregnant or lactating or intending to become pregnant during the study, or within 30 days after the last dose of study drug. Female subjects of child-bearing potential must have a negative urine pregnancy test result at Week 26 of Study HZNP-ACT-302 and agree to use a reliable method of contraception throughout the study and for 30 days after the last dose of study drug.

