3. OVERALL STUDY DESIGN AND PLAN

This is a multi-center, open-label, long-term safety extension study of ACTIMMUNE in the treatment of FA in children and young adults. Subjects who complete 26 weeks of treatment in HZNP-ACT-302 will be eligible for enrollment in this study. The sample size is not based on statistical considerations.

The overall maximum treatment duration for an individual subject is open-ended and treatment will continue until ACTIMMUNE is commercially available for the treatment of FA in the US or until the Sponsor decides to discontinue development for this indication. The initial dose of ACTIMMUNE will be individualized for each subject and will be determined by the investigator, provided that the initial dose does not exceed the maximum tolerated dose in HZNP-ACT-302. The investigator may subsequently adjust the dose for any subject if deemed clinically appropriate, provided that the dose does not exceed 100 μ g/m2. All doses of ACTIMMUNE will be administered by subcutaneous injection three times a week (TIW) at home.

Protocol: HZNP-ACT-303 Page 9 of 19

Final Version 1.0

Table 1.Schedule of Events

Study Phase	Treatment Period			End-of-Study
	Baseline ⁶	3-Month Visits ⁸	6-Month Visits	or Premature Withdrawal ¹⁰
Study Days (± visit window)	Day 1 (Week 28 of Study HZNP-ACT-302)	90 (± 7) Days after Last Visit	Every 180 (± 14) Days	
Informed consent/assent	X			
Medical history ¹	X			
Review of inclusion/exclusion criteria	X			
Dispense study drug ²	X	X^9	X	
Drug compliance ³		X^9	X	X
TEAE, SAE assessment ⁴	X^7	X	X	X
Brief physical examination	X^7		X	X
Vital Signs: blood pressure, pulse, temperature	X		X	X
Clinical laboratory evaluation (hematology, chemistry, urinalysis)	X		X	X
Electrocardiograms				X ¹¹
Urine pregnancy test ⁵	X		X	X
FARS				X ¹¹
Prior/concomitant medications	X^7	X	X	X

SAE=serious adverse event, TEAE=treatment-emergent adverse event.

- ³ Subjects will be instructed to return all used and unused study drug vials at each clinic visit.
- ⁴ Adverse events occurring or worsening on or after the date of administration of the first dose of study drug through the end of the study will be considered treatment-emergent adverse events (TEAEs). All serious adverse events (SAEs) that occur on or after the date of administration of the first dose of study drug through two weeks after study discontinuation will be considered treatment-emergent SAEs (TESAEs) and will be recorded and reported to Horizon drug safety.

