6. GENERAL ISSUES FOR STATISTICAL ANALYSIS

Data processing, tabulation of descriptive statistics, calculation of inferential statistics, and graphical representations will be performed using SAS® Software (release 9.3 or higher) for Windows, unless otherwise specified.

Continuous (quantitative) variables will be summarized using descriptive statistics including number of non-missing values, mean, standard deviation (SD), median, minimum, and maximum.

Categorical (qualitative) variables will be summarized using the number and proportion of each possible value. In general, the denominator for the percentage calculation will be based upon the total number of subjects in the study population for the treatment group.

The minimum and maximum will be reported with the same degree of precision (i.e., the same number of decimal places) as the raw data. Measures of location (mean and median) will be reported to 1 degree of precision more than the raw data and measures of spread (standard deviation) will be reported to two degrees of precision more than the raw data.

Assessments done on unscheduled visits will not be summarized but will be listed. All analyses will be completed on the Safety Population unless otherwise specified. Additionally, all summaries will be presented by overall treatment.

All final, planned analyses identified in the protocol and in this SAP will be performed after all relevant study data have been processed and integrated into the analysis database, analysis populations have been finalized, and the database has been locked. Any post-hoc, exploratory

Protocol: HZNP-ACT-303 Page 11 of 19

Final Version 1.0

analysis completed to support planned study analyses, which were not identified in this SAP, will be documented and reported in Section 9.8 of the CSR. Any results from these unplanned analyses (post-hoc) will also be clearly identified as subject in the text of the CSR.

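### SAP 9.3 shows weight and height only as pooled raw values and changes, so expected growth can offset slowed gain or weight loss arising after the 303 baseline

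*SAP*

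**What the plan says.** SAP 9.3 reads "Descriptive summaries of actual (absolute) values and changes from baseline will be presented for all vital signs". The sentence then names temperature, blood pressure and heart rate, adds weight, height and BSA, and groups everything by visit and overall treatment. A by-subject listing follows. SAP 6 sets the general rule: "all summaries will be presented by overall treatment". The age bands 10 to 16 and 17 and above appear only in SAP 7.3, in the demographics table built from HZNP-ACT-301 data. SAP 9.3 has no standardised score, percentile or age breakdown.

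The neighbouring sections do give a reference frame. Laboratory values get normal ranges and shift tables (SAP 9.2), and ECGs get normal and abnormal categories with shift tables (SAP 9.4).

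The reference point for change is in SAP 6.3: "303 Baseline = The last non-missing measurement/assessment on the date of Week 26" of HZNP-ACT-302. If that value is missing, the last value on or before the first 303 dose is used. Protocol 8.6.1 describes Week 26 as the last visit on treatment in 302. On duration, SAP 3 says "The overall maximum treatment duration for an individual subject is open-ended". Protocol 8.4.8 gives every subject the study drug.

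The Protocol 2.1 schedule row is "Vital Signs: blood pressure, pulse, temperature". Weight and height are listed neither there nor in Protocol 8.5.2.3.

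**The concern.** In an adult population, a mean raw weight change near zero reasonably reads as stability. In a growing subject it does not: no gain over a year is a departure from what was expected, yet it is tabulated as no change. With one arm and one pooled column, the summary contains nothing to subtract expected growth.

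This matters for weight because the label in Protocol 16.2 lists decreased weight among potentially related reactions (label 6.1). It calls toxicity dose-dependent and does not recommend doses above 50 mcg/m² (label 2.3), whereas this study allows up to 100 µg/m². Long-term safety is the only objective. The same label (6.2) judged height and weight against national normative scales in an uncontrolled group of young CGD patients. SAP 9.3 plans no such comparison here. What is at stake is a readable summary of slowed growth in a long-term paediatric safety report.

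**Working it through.** The plan gives no figure to reproduce, so the check is one identity with declared assumptions.

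**From the documents**
- Subjects complete 26 weeks in 301 and then 26 weeks in 302 (Protocol 6.2; Protocol 8.3.1: "Completed 26 weeks of treatment and the Week 28 Follow-Up Visit in Study HZNP-ACT-302"). So 303 baseline falls at least 26 + 26 = 52 weeks after 301 baseline.
- A subject aged 10 to 16 at 301 baseline is therefore about 11 to 17 at 303 baseline.
- By then the subject has had 26 weeks of drug, or about 52 weeks if on active drug in 301.

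**Assumed, because the documents are silent**
- f, the share of subjects still growing: 0.4 to 0.8.
- g, yearly weight gain in those subjects: 1 to 5 kg.
- s, the reference SD of weight at a given age and sex: 8 to 14 kg, held constant over time.

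**Pooled mean.** Let T be years since 303 baseline, d0 the weight loss already present at that baseline, and d1 the further loss arising after it, equal in all subjects. The loss d0 is in both values and cancels, so

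mean raw change = f × g × T − d1,

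which is zero when d1 = f × g × T.

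| T | Lowest offset | Highest offset |
|---|---|---|
| 1 year | 0.4 × 1 × 1 = 0.4 kg | 0.8 × 5 × 1 = 4.0 kg |
| 2 years | 0.4 × 1 × 2 = 0.8 kg | 0.8 × 5 × 2 = 8.0 kg |

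**Sensitivity to other assumptions.** Take f from 0.25 to 0.75, g from 2 to 6 kg a year, and a loss of 1.5 kg in every subject. At one year the displayed mean runs from 0.25 × 2 − 1.5 = −1.0 kg to 0.75 × 6 − 1.5 = +3.0 kg. The same loss can appear as a fall, no change or a rise, depending on the unknown age mix.

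**One growing subject who stops gaining.** Raw change is 0 kg. The standardised score changes by about −g × T / s:
- one year: −1/14 = −0.07 to −5/8 = −0.63;
- two years: −2/14 = −0.14 to −10/8 = −1.25.

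**What the planned output still shows.** At the top of the range (f = 0.8, g = 5, d1 = 4, T = 1), growing subjects each gain 5 − 4 = 1 kg and the others each lose 4 kg. The mean is 0.8 × 1 − 0.2 × 4 = 0, but the minimum is −4 kg and the listing shows who lost weight. The slowed gain in the other 80% looks like a modest rise.

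**The case against.** The strongest objection is that the example rests on data the protocol does not schedule. Weight and height are absent from the schedule, the vital-sign definition and the visit procedure lists, and BSA dosing (Protocol 8.4.7.2) sets no interval for re-measurement. This stands as a limit on the fix, since the added table may be sparse. It does not remove the point: the SAP, written after review of the eCRFs, commits to tabulating both by visit, and standardising whatever is recorded needs no new data.

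The planned output is also not blind. Height change sits beside weight change, so flat weight with rising height can be noticed. The minimum and listing expose individual losses, and clinically significant loss can be reported as an adverse event. This is real but partial protection, because none of it summarises slowed growth.

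Every magnitude is assumed, and the weight range at one year spans a factor of ten. That is correct. The label's only growth evidence is reassuring, but it concerns CGD patients under 3 years in uncontrolled studies.

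A reader might infer three stronger claims that the documents do not support.
- *Pulse and blood pressure are masked too.* The documents give no growth trend for either. With assumed yearly trends of 0.5 to 2 bpm and 1 to 2 mmHg, the one-year offset is only 0.4 × 0.5 = 0.2 to 0.8 × 2 = 1.6 bpm, and 0.4 × 1 = 0.4 to 0.8 × 2 = 1.6 mmHg. A table of values outside age-specific limits would not detect this. For a +2 SD limit, P(Z > 2 − 1.6/SD) − P(Z > 2) is 0.6 to 1.3 percentage points for an assumed SD of 15 to 8 bpm.
- *Growth hides all drug effects since treatment began.* Effects present at 302 Week 26 cancel from the change whatever growth does. Where the fallback baseline applies, the value may be from Day 1, two weeks after the last on-treatment visit, so cancellation is then less certain.
- *A falling standardised score would show a drug effect.* FA itself brings scoliosis and progression, and there is no control arm.

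**Conclusion.** The point holds for weight and height, and chiefly for weight. The pooled raw change in SAP 9.3 cannot separate expected growth from slowed gain or weight loss that begins or worsens after the 303 baseline. This depends on some subjects still growing, which the age bands in SAP 7.3 make very likely. The size is not derivable; the calculated offsets are illustrations under stated assumptions. Nothing planned is incorrect, and in a descriptive, abbreviated safety report no inference is affected. This is a worthwhile refinement, not a defect that threatens the study's conclusions.

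**What to change.** Keep the raw tables and add to SAP 9.3: *For subjects within the reference-chart age range, age- and sex-standardised weight and height, and their change from 303 baseline, will be summarised by visit wherever values are recorded.* Name the reference in the SAP before database lock.

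Change from 301 baseline may be shown beside it, since SAP 7.3 already tabulates 301 weight and height. Label that column as mixing placebo and active exposure in 301.

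The cost is SAP wording and a little programming, with no new visits or procedures. The downsides should be stated with the table. Counts may be small or patchy, subjects above the chart range drop out, and scoliosis or FA progression can also move the scores. The text should say that the scores describe departure from expected growth and do not attribute it to the drug. No change to the pulse or blood pressure tables is needed on this ground.
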